**Table 8: TJ004309 Treatment Management Guidelines for Immune-Related Adverse Events (irAEs)**

General instructions:

1. Severe and life-threatening irAEs should be treated with IV corticosteroid followed by oral steroids. Other immunosuppressive treatment should begin if the irAEs are not controlled by corticosteroids.
2. TJ004309 must be permanently discontinued if the irAE does not resolve or the corticosteroid dose is not  $\leq 10$  mg/day within 12 weeks of the last treatment.
3. The corticosteroid taper should begin when the irAE is  $\leq$  Grade 1 and continue tapering at least 4 weeks.
4. If TJ004309 has been withheld, TJ004309 may resume after the irAE decreased to  $\leq$  Grade 1 after corticosteroid taper.

irAEs	Toxicity Grade (CTCAE V5.0)	Action with TJ004309	Corticosteroid and/or other therapies	Monitoring and Follow-up
Pneumonitis	Grade 2	Withhold	Administer corticosteroids (initial dose of 1 to 2 mg/kg prednisone or equivalent) followed by taper Add prophylactic antibiotics for opportunistic infections	Monitor participants for signs and symptoms of pneumonitis Evaluate participants with suspected pneumonitis with radiographic imaging and initiate corticosteroid treatment
	Recurrent Grade 2, Grade 3 or 4	Permanently discontinue		
Diarrhea / Colitis	Grade 2 or 3	Withhold	Administer corticosteroids (initial dose of 1 to 2 mg/kg prednisone or equivalent) followed by taper	Monitor participants for signs and symptoms of enterocolitis (ie, diarrhea, abdominal pain, blood or mucus in stool with or without fever) and of bowel perforation (ie, peritoneal signs and ileus) Participants with $\geq$ Grade 2 diarrhea suspecting colitis should consider GI consultation and performing endoscopy to rule out colitis Participants with diarrhea/colitis should be advised to drink liberal quantities of clear fluids. If sufficient oral fluid intake is not feasible, fluid and electrolytes should be substituted via IV infusion
	Recurrent Grade 3 or Grade 4	Permanently discontinue		
AST or ALT elevation or Increased Bilirubin	Grade 2 a	Withhold	Administer corticosteroids (initial dose of 0.5 to 1 mg/kg prednisone or equivalent) followed by taper	Monitor with liver function tests (consider weekly or more frequently until liver enzyme value returned to baseline or is stable)

	Grade 3 b or 4 c	Permanently discontinue	Administer corticosteroids (initial dose of 1 to 2 mg/kg prednisone or equivalent) followed by taper	
Type 1 diabetes mellitus (T1DM) or Hyperglycemia	New onset T1DM or Grade 3 or 4 hyperglycemia associated with evidence of β-cell failure	Withhold d	Initiate insulin replacement therapy for participants with T1DM  Administer antihyperglycemic in participants with hyperglycemia	Monitor participants for hyperglycemia or other signs and symptoms of diabetes
Hypophysitis	Grade 2	Withhold	Administer corticosteroids and initiate hormonal replacements as clinically indicated	Monitor for signs and symptoms of hypophysitis (including hypopituitarism and adrenal insufficiency)
	Grade 3 or 4	Withhold or permanently discontinue d		
Hyperthyroidism	Grade 2	Continue	Treat with nonselective beta-blockers (e.g., propranolol) or thionamides as appropriate	Monitor for signs and symptoms of thyroid disorders
	Grade 3 or 4	Withhold or permanently discontinue d		

Hypothyroidism	Grade 2, 3 or 4	Continue	Initiate thyroid replacement hormones (e.g., levothyroxine or liothyronine) per standard of care	Monitor for signs and symptoms of thyroid disorders
Nephritis: grading according to increased creatinine or acute kidney injury	Grade 2	Withhold	Administer corticosteroids (prednisone 1 to 2 mg/kg or equivalent) followed by taper	Monitor changes of renal function
	Grade 3 or 4	Permanently discontinue		
Neurological Toxicities	Grade 2	Withhold	Based on severity of AE administer corticosteroids	Ensure adequate evaluation to confirm etiology and/or exclude other causes
	Grade 3 or 4	Permanently discontinue		
Myocarditis	Grade 2, 3 or 4	Permanently discontinue	Based on severity of AE administer corticosteroids	Ensure adequate evaluation to confirm etiology and/or exclude other causes
Exfoliative Dermatologic Conditions	Suspected SJS, TEN, or DRESS	Withhold	Based on severity of AE administer corticosteroids	Ensure adequate evaluation to confirm etiology and/or exclude other causes
	Confirmed SJS, TEN, or DRESS	Permanently discontinue		
All other irAEs	Persistent Grade 2	Withhold		Ensure adequate evaluation to confirm etiology and/or exclude other causes

	Grade 3	Withhold or discontinue based on the event e	Based on severity of AE administer corticosteroids	
	Recurrent Grade 3 or Grade 4	Permanently discontinue		

AE(s)=adverse event(s); ALT= alanine aminotransferase; AST=aspartate aminotransferase; CTCAE=Common Terminology Criteria for Adverse Events; DRESS=Drug Rash with Eosinophilia and Systemic Symptom; GI=gastrointestinal; IO=immuno-oncology; ir=immune related; IV=intravenous; SJS=Stevens-Johnson Syndrome; T1DM=type 1 diabetes mellitus; TEN=Toxic Epidermal Necrolysis; ULN=upper limit of normal.

Note: Non-irAE will be managed as appropriate, following clinical practice recommendations.

a AST/ALT: > 3.0 - 5.0 x ULN if baseline normal; > 3.0 - 5.0 x baseline, if baseline abnormal; bilirubin: > 1.5 - 3.0 x ULN if baseline normal; > 1.5 - 3.0 x baseline if baseline abnormal

b AST/ALT: > 5.0 to 20.0 x ULN, if baseline normal; > 5.0 - 20.0 x baseline, if baseline abnormal; bilirubin: > 3.0 - 10.0 x ULN if baseline normal; > 3.0 - 10.0 x baseline if baseline abnormal

c AST/ALT: > 20.0 x ULN, if baseline normal; > 20.0 x baseline, if baseline abnormal; bilirubin: > 10.0 x ULN if baseline normal; > 10.0 x baseline if baseline abnormal

d The decision to withhold or permanently discontinue TJ004309 is at the discretion of the investigator or treating physician. If control achieved or  $\leq$  Grade 2, TJ004309 may be resumed.

e Events that require discontinuation include but are not limited to: encephalitis and other clinically important irAEs (eg. vasculitis and sclerosing cholangitis).

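### Table 8 gives inconsistent conditions for restarting withheld TJ004309 after certain immune-related endocrine events, most clearly for hypophysitis that improves from Grade 3 to Grade 2

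*Protocol*

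**What the plan says.** All of the following is in the current text of Protocol Section 6.9, Table 8.

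- **General instruction 2:** "TJ004309 must be permanently discontinued if the irAE does not resolve", or if the corticosteroid dose has not come down to 10 mg/day or less, within 12 weeks of the last treatment.
- **General instruction 3:** "The corticosteroid taper should begin when the irAE is" at most Grade 1, and the taper runs for at least 4 weeks.
- **General instruction 4:** "If TJ004309 has been withheld, TJ004309 may resume after the irAE decreased to" at most "Grade 1 after corticosteroid taper".
- **Hypophysitis, lower grade:** "Hypophysitis Grade 2 Withhold". This entry carries no footnote. The treatment column for hypophysitis reads: "Administer corticosteroids and initiate hormonal replacements as clinically indicated".
- **Rows with footnote d:** type 1 diabetes or hyperglycemia (withhold), Grade 3 or 4 hypophysitis and Grade 3 or 4 hyperthyroidism (both withhold or permanently discontinue).
- **Footnote d:** "The decision to withhold or permanently discontinue TJ004309 is at the discretion of the investigator or treating physician". It then adds that if control is achieved or the event is at most "Grade 2, TJ004309 may be resumed".

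The Grade 2 hyperthyroidism row says to continue. The body of Section 6.9 refers immune-related events to Table 8, and uses recovery to Grade 1 or lower, or baseline, as its own general criterion for continuing treatment.

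**The concern.** A site managing one of the three footnote-d events finds two restart conditions in one table and nothing that ranks them. One is met at Grade 2, or at control without a stated grade. The other is not met until Grade 1 or lower after taper. For hypophysitis, the event's own Grade 2 entry adds a third statement that points away from dosing.

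Two sites could therefore treat identical patients differently while each believes it is following the protocol. This is first a safety matter, because the instruction governs re-exposure after a severe immune-related event in a combination with a PD-L1 antibody. It is also a matter of consistent conduct, since holding or resuming changes the dosing that SAP Section 7 summarizes.

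**Working it through.** No sample size, power or event count is involved, so the check is a side-by-side reading. Take a patient whose TJ004309 was withheld for a Grade 3 event that has now improved to Grade 2.

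| Event | Footnote d | General instruction 4 | Event's own Grade 2 row |
|---|---|---|---|
| Hypophysitis | Restart permitted | Not yet permitted | Withhold |
| Hyperthyroidism | Restart permitted | Not yet permitted | Continue |
| Diabetes/hyperglycemia | Restart permitted | Not yet permitted | No such row |

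**Step 1: footnote d against instruction 4.** The ceilings are Grade 2 and Grade 1, a difference of 2 − 1 = 1 CTCAE grade. At Grade 2 the first condition is met and the second is not. This holds for all three events.

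**Step 2: the taper.** Under instruction 3 the taper starts only at Grade 1 or lower, so a patient still at Grade 2 who is on corticosteroids has not started it and fails both parts of instruction 4. If that instruction requires a completed taper (an assumption about its wording), the further wait is at least 4 × 7 = 28 days, against a 21-day cycle. At least one scheduled dose would then be missed after Grade 1 is reached. This applies where corticosteroids are used, as the hypophysitis row provides.

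**Step 3: the event's own Grade 2 row.** Only hypophysitis conflicts here. For hyperthyroidism the Grade 2 row agrees with footnote d. Diabetes/hyperglycemia has no Grade 2 row. Hypothyroidism is continued at Grades 2 to 4 and carries no footnote d, so it is not affected.

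**Step 4: instruction 2.** Footnote d allows a restart when control is achieved. Instruction 2 requires permanent discontinuation when the event does not resolve within 12 weeks. Neither control nor resolution is defined. The diabetes row provides for insulin replacement, so control without disappearance of the condition is foreseeable, and the table does not say whether that counts as resolved.

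**Step 5: how often.** Protocol Table 4 lists events suspected to be related to TJ004309 that occurred in more than 1 of 20 Phase 1 patients. Hyperthyroidism appears in 2 of 20 (10%), one Grade 1 and one Grade 2. Hypophysitis and diabetes are not listed, which is compatible with 0 or 1 patient each. The rate of Grade 3 or 4 endocrine events in this trial is not given.

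**The case against.** The best defence is that footnote d was meant as an exception. It is attached to only three endocrine entries, and a taper condition fits two of them poorly: the diabetes/hyperglycemia row prescribes insulin or antihyperglycemic drugs, and the hyperthyroidism row beta-blockers or thionamides, with no corticosteroid in either. The hypophysitis Grade 2 row could also be read as the action for an event that first presents at Grade 2, leaving improvement from a higher grade to footnote d. Together these two readings would remove the conflicts with instruction 4 and with that row. They are plausible, but the table states neither, and instructions 2 and 4 contain no exception. Hypophysitis is also the footnote-d event for which corticosteroids are prescribed, so the taper condition does fit it.

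A second defence is discretion. Footnote d gives the physician the choice between withholding and permanent discontinuation, and the body of Section 6.9 has a general sentence on managing patients by medical judgment. The discretion note under Tables 6 and 7 is missing from Table 8, but that absence alone proves little given the general sentence. What remains is that the discretion in footnote d does not say which restart condition applies, and Section 6.9 also forbids withholding other than as it describes.

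A third point stands in full: both restart statements are permissions. An investigator who waits for Grade 1 after taper breaches neither. The inconsistency is that one statement permits dosing at a point where another does not yet permit it and, for hypophysitis, a third says to withhold.

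The Grade 1-or-baseline criterion in the body of Section 6.9 is weak support, because that section sends immune-related events to Table 8. The point does not depend on it.

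**Conclusion.** Table 8 is internally inconsistent on restarting TJ004309. For all three footnote-d events, footnote d and general instruction 4 differ by one grade, and instruction 4 adds a taper condition. For hypophysitis alone, the event's own Grade 2 row also conflicts. The conclusion rests on reading the general instructions as applying to every row, which is what their wording says in the absence of an exception.

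A reader might infer more than the documents support:

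- *That TJ004309 is restarted at Grade 2.* The text only says that it may be.
- *That every footnote-d event meets a three-way conflict.* Only hypophysitis does.
- *That controlled diabetes must be both resumed and permanently stopped.* This requires *resolve* to mean complete disappearance. The term is undefined, and instruction 4 itself accepts residual Grade 1 toxicity. The relation between control and resolution is unclear, which is a lesser defect than a proven contradiction.
- *That the response rate or the discontinuation rate will be distorted.* Neither is shown. A hold does not in itself end treatment, so it does not close the best-response window in SAP Section 8.1.

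The number of patients affected is unknown and probably low. Cohorts are capped at 30, the related Phase 1 hyperthyroidism was Grade 1 or 2, and SAP Section 4.1 reports that Part 2 was not initiated. The documents do not say whether any patient is still being dosed. The reason to act is safety and consistent conduct, together with the risk of carrying the table into a later protocol.

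**What to change.** The sponsor's clinical team should reconcile four places in Table 8: footnote d, general instructions 2 and 4, and the hypophysitis Grade 2 row. After the change:

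- each footnote-d event has one stated restart condition;
- the table says explicitly whether footnote d is an exception to the general instructions and, if it is, instructions 2 and 4 say so too;
- the hypophysitis Grade 2 row says whether it covers an event improving from Grade 3 or 4 as well as one presenting at Grade 2;
- *control* and *resolve* are defined well enough to show how an event that is controlled but persistent is handled under instruction 2.

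Which threshold applies is a clinical decision, and none is proposed here. The cost is a wording change through a protocol amendment or clarification letter, with no added patients, procedures or analyses.

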## **6.10 Treatment after Disease Progression**

A patient who is deriving clinical benefit despite radiological evidence of progressive disease, defined by RECIST 1.1 and iRECIST criteria, may continue study treatment at the Investigator's discretion after discussion with the Sponsor. The patient must meet all of the following criteria:

- ECOG status of 0 or 1
- Absence of signs/symptoms (including laboratory values) indicating unequivocal progression of disease.
- Absence of tumor progression at specific anatomical sites that cannot be readily managed and stabilized by protocol-allowed medical interventions prior to repeat dosing. These anatomical sites include the CNS, and other organs/tissues where compromised function secondary to tumor progression would be expected to result in severe and/or irreversible disability or death.
- Must provide consent to acknowledge discussion with the Investigator of the benefit-risk of continuing on study beyond radiographic progression.

## **6.11 Intervention after the End of the Study**

No intervention following the completion of study participation is planned.

## 7 DISCONTINUATION OF STUDY INTERVENTION AND PARTICIPANT DISCONTINUATION/WITHDRAWAL

### 7.1 Discontinuation of Study Intervention

Patients will be informed that they have the right to discontinue study drug at any time for any reason, without prejudice to their medical care. At the time of discontinuation, all study procedures outlined for the EOS visit should be completed (see [Table 2](#)). The primary reason for study drug discontinuation is to be recorded in the eCRF.

#### 7.1.1 Reasons for Discontinuation of Study Intervention

The Investigator has the right to discontinue study drug for any of the following reasons:

- Progression of disease that, in the opinion of the Investigator, precludes further study treatment. (After consultation with the Study Responsible Physician, study drug may be continued for a patient who has met the criteria for progressive disease (PD) but, in the Investigator's opinion, is receiving benefit)
- Occurrence of an unacceptable AE per the Investigator medical judgement
- Pregnancy (see [Section 8.4.8](#))
- Non-compliance
- Lost to follow-up
- Patient withdrawal of consent
- Sponsor request

### 7.2 Replacement of Patients

Subjects who are withdrawn for reasons not related to study drug may be replaced following discussion between the Investigator and the Sponsor.

### 7.3 Participant Withdrawal from the Study

A participant may withdraw from the study at any time at his/her own request or may be withdrawn at any time at the discretion of the Investigator for safety, behavioral, compliance, or administrative reasons.

At the time of withdrawal from the study, if possible, an EOS visit should be conducted, as shown in the SoA ([Table 2](#)). See [Table 2](#) for data to be collected at the time of study withdrawal and follow-up and for any further evaluations that need to be completed.

If the participant withdraws consent, the patient will be permanently discontinued from the study drug and withdrawn from the study at that time. The Sponsor may retain and continue to use any data collected before such a withdrawal of consent.

If a participant withdraws from the study, he/she may request destruction of any samples taken and not tested, and the Investigator must document this in the site study records.

#### **7.4 Lost to Follow up**

A patient will be considered lost to follow-up if he or she repeatedly fails to return for scheduled visits and is unable to be contacted by the study center.

The following actions must be taken if a patient fails to return to the clinic for a required study visit or following the site's standard procedures:

- The site must attempt to contact the patient and reschedule the missed visit as soon as possible and counsel the participant on the importance of maintaining the assigned visit schedule and ascertain whether or not the patient wishes to and/or should continue in the study.
- Before a patient is deemed lost to follow-up, the Investigator or designee must make every effort to regain contact with the participant (where possible, 3 telephone calls and, if necessary, a certified letter to the participant's last known mailing address or local equivalent methods). These contact attempts should be documented in the patient's medical record.
- Should the patient continue to be unreachable, he/she will be considered to have withdrawn from the study.

Discontinuation of specific sites or of the study as a whole will be handled as described in [Section 7](#).

## 8 STUDY ASSESSMENTS AND PROCEDURES

Study procedures and their timing are summarized in the SoA ([Table 2](#) and [Table 3](#)).

Immediate safety concerns should be discussed with the Sponsor immediately upon occurrence or awareness to determine if the patient should continue or discontinue study drug.

Adherence to the study design requirements, including those specified in the SoA, is essential and required for study conduct.

All screening evaluations must be completed and reviewed to confirm that a potential patient meets all eligibility criteria. The Investigator will maintain a screening log to record details of all participants screened and to confirm eligibility or record reasons for screening failure, as applicable.

The patient/patient's health proxy must provide written informed consent before the performance of any study-specific procedures.

Procedures conducted as part of the patient's routine clinical management (e.g., blood count) and obtained before signing of the informed consent form (ICF) may be utilized for screening or baseline purposes provided the procedures met the protocol-specified criteria and were performed within the time frame defined in the SoA ([Table 2](#)).

### 8.1 Efficacy Assessments

Tumors will be assessed for anti-tumor activity of TJ004309 at times indicated in the SoA ([Table 3](#)). Assessments will be measured by BOR, ORR, DOR, PFS, and OS and will be based on RECIST 1.1 and iRECIST for solid tumors.

### 8.2 Baseline and Safety Assessments

Planned time points for all safety assessments are provided in the SoA ([Table 2](#)).

#### 8.2.1 Demographics

Patient demographics, including age, sex, race, and ethnicity, are to be documented during Screening.

#### 8.2.2 Medical History, Including Cancer History

A complete medical history is to be documented during Screening and updated at Baseline, prior to administration of the first study drug dose.

The medical history is to include cancer history, including the patient's primary diagnosis, date of diagnosis, method of diagnosis, and all previous treatments, including radiation therapy, and response to such treatment.

### 8.2.3 Physical Examinations, Height, and Weight

A full physical examination will be performed at Screening and at pre-dose of Cycle 1 Day 1, unless the screening physical examination was performed within the last 7 days. The full physical examination includes general appearance, head/ears/eyes/nose/throat, lungs/chest, heart, abdomen, lymph nodes, musculoskeletal, extremities and neurological examinations. The genitourinary examination is considered optional unless indicated by medical history or report of current condition.

Starting with Cycle 2, abbreviated physical examinations should be performed as appropriate at each visit in which completed physical examinations are not required, and on an as needed basis for assessment of AEs. Abbreviated physical examinations should be targeted to specific symptoms or complaints and be consistent with local standard of care (brief physical examination will be symptom-directed and include assessment of cardiac, respiratory, and gastrointestinal systems).

Investigators should pay special attention to clinical signs related to previous serious illnesses.

Height (cm) is to be measured for all patients at Screening only.

Weight (kg) is to be measured for all patients at the designated time points in the SoA ([Table 2](#)). The dose of each study drug will be calculated based on the actual weight of each subject, as measured at the screening visit. The weight used may be revised to a weight collected at a later date if it has changed by more than 10%.

### 8.2.4 Vital Signs

Seated blood pressure, seated pulse rate, respiratory rate, and body temperature will be assessed at the times indicated in the Schedule of Assessments in [Table 2](#).

For the first cycle, vital signs (seated blood pressure, seated pulse rate, respiratory rate) will be collected pre-dose, 30 minutes after the start of infusion, and 2 hours after EOI. Body temperature will be measured singly. The median value will be used as the baseline value in the data analysis. For treatment in Cycle 1, subjects should remain at the site for monitoring (with immediate access to medical resuscitation equipment) for at least 1 hour following the end of the initial infusion.

At all subsequent cycles vital signs will be performed pre-dose singly and repeated once if outside the relevant clinical reference ranges. Vital signs may also be performed at other times if judged to be clinically appropriate or if the ongoing review of the data suggests a more detailed assessment of vital signs is required.

Subjects must be seated for at least 5 minutes before blood pressure and pulse rate measurements.

